Following signed consent participants will be asked to complete a few baseline tasks to be fully eligible for participation in the study. These tasks include three days of food tracking using ASA-24, baseline surveys, submission of cooking frequency and food photos, and finally a one-on-one interview with study staff to discuss their participation. These baseline tasks are intended to ensure participant compliance and retention during the 18-week intervention.

Eligible participants will be assigned to one of four scheduled class periods based on their stated availability or recruited for the control condition. Once all classes are full, a random assignment table will be used to determine the group assignment for each class period. Participants will then be informed of their group assignment (active with follow up or active no follow up). Participants who are in the control condition will be randomly assigned to either a group that receives follow-ups or a group that does not. Groups will not be stratified by any criteria, and instead will be determined based upon participant availability.

Surveys will be administered through the study REDCap website at baseline and study end. Participants will receive links to the questionnaires and reminders to complete questionnaires via email. These measures are outlined in greater detail below. In addition to questionnaires, weekly data collection (Photo Elicitation and Cooking Frequency) will be administered through REDCap. Participants will receive a weekly email with links to a REDCap data collection tool. Participants will receive reminders to complete weekly data submissions, and will be given information regarding a helpline for using the study website and data entry.

Table 1 outlines when each measure will occur during the study.

Measures	Baseline	Weekly	Phase 1	Phase 2	Phase 3
ASA24					
HEI (calculated)					
CAFPAS					
Cooking Perceptions and Behaviors					
PSS					
Intuitive Eating Scale					
Interoceptive Awareness					
Cooking Frequency					
Photo Elicitation					
Class Evaluation					
Meal Kit Evaluation				X	
COVID-19 Questionnaire					X

Quantitative Measures

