Interoceptive Awareness - Research has indicated that there is an association between interoceptive awareness and intuitive eating. Interoceptive awareness is the ability to detect internal bodily cues.^{46,47} One way to measure interoceptive awareness in individuals is to determine their ability to count the number of times they perceive their heart to beat during a given period of time.⁴⁶ We will ask subjects to perceive their heartbeat for 30 seconds, and then report their result. Next, we will take their wrist pulse for 30 seconds. We will compare heartbeat perception accuracy to Intuitive Eating scores, to determine any association in college aged students. Participants will be asked if they would like to complete the interoceptive Awareness exercise during phase I cooking classes, but may opt not to participate.

Weekly Assessment of Cooking Frequency: Each week, participants will complete a brief survey to record how many times that week they cooked at home. The weekly surveys should take 5 minutes or less to complete.

COVID-19 Questionnaire – At the conclusion of the study all participants will be asked to answer questions related to changes that occurred to their living situation and food access as a result of the COVID-19 outbreak and subsequent social-distancing measures.

Qualitative Measures

Photo Elicitation – Using photo elicitation, participants take photos of a particular topic and then these photos are used as the starting point for an interview between the participant and researcher. Photo elicitation has been used in public health research previously with a variety of projects and populations.⁴⁸ For this study, participants will be asked to take photos with their smartphones or cameras and then upload two photos each week to REDCap via the weekly email link. Instructions will ask participants to capture the meal that week they feel most represents their interpretation of a "healthy meal," and the meal they ate that week that *least* represents their interpretation of a "healthy meal." Both the intervention and control group will be instructed to take these weekly photos and label them as a meal they cooked at home or a meal they did not cook at home. At

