After the final cooking class, participants in groups B and D will receive no further instruction, though they will be asked to complete surveys and data collection through the remainder of the study phases. Phase 2 will begin in mid-January 2020. Participants in Groups A and C will receive weekly meal kit deliveries for 6 weeks. Meal kits will be delivered to students’ homes once per week and will include the ingredients and instructions for preparing 3 separate meals. Phase 3 will be immediately following phase 2. Participants in groups A and C will receive an email at the beginning of each week for the next six weeks that provides them with 5 healthy recipes developed by the study team. Students will generally receive the same recipes though; modifications may be made for participants with special dietary restrictions.

Facilities and Equipment Needed

Cooking Labs – The cooking classes and demonstrations will take place in the Nutrition and Food Sciences teaching kitchen located in the Marsh Life Science building. The teaching kitchen has room for 16 students to complete hands on cooking labs, and an additional space where students can get directions, eat, and watch cooking demos. The kitchens are fully stocked with the necessary kitchen equipment.

Follow-up Data Collection

Participants will be alerted by email to complete their follow-up assessment questionnaires which are anticipated to take approximately 30 minutes to complete and 3 days of the ASA24 (approximately 30 minutes per day).

All participants will be offered small incentives such as cooking equipment, cookbooks, gift cards, etc. (valued at approximately \$ 5-25) after completion of the follow-up data collection. Those in the Control Group will also receive a small incentive for completing their baseline measures.

For research involving survey, questionnaires, etc.: Describe the setting and the mode of administering the instrument and the provisions for maintaining privacy and confidentiality. Include the duration, intervals of administration, and overall length of participation. (describe and attach all instruments)

Not applicable

Questionnaires and ASA-24 logs will be administered at baseline and at the end of each study phase.

Photo elicitations and cooking frequency surveys will be administered weekly during the active study phases.

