Surveys questionnaires, and photo elicitations will be administered online through the study website (REDCap). Participants will be sent links to questionnaires and surveys through their email. Participants will be able to save and return to questionnaires with a unique 8 digit ID provided by REDCap, however participants will not have access to review the questionnaires after completion or to make changes after submitting the forms. They will be provided with a helpline contact should they encounter difficulty in completing the forms. If participants prefer, they can complete the forms using a paper copy rather than online. It is expected that the online baseline and follow-up assessment questionnaires will take less than 30 minutes to complete.

ASA-24 logs will be administered through the ASA-24 respondent website. Each participant will have a unique ID and password that will be used to log in to the website. Participants will be provided with an ASA-24 Getting Started Guide and a helpline should they have trouble using the website. The baseline and follow-up ASA24 3 day tracking is estimated to take approximately 30 minutes for each entry.

Surveys, questionnaires, and ASA-24 logs will all be identified by a unique study ID number. Participant names and other identifying information will not appear on any materials except for the initial study application. The name field will be flagged as an identifier in REDCap so that it may be excluded from data analysis. A password-protected master key will be maintained solely by the research coordinator and PI.

Statistical Considerations: *Delineate the precise outcomes to be measured and analyzed. Describe how these results will be measured and statistically analyzed. Delineate methods used to estimate the required number of subjects. Describe power calculations if the study involves comparisons. Perform this analysis on each of the primary and secondary objectives, if possible.*

Aim 1: To pilot test a food-agency focused cooking class pedagogy to motivate college students to cook more frequently, improve their diet quality, and increase their sense of food agency.

Hypothesis 1. Students in the intervention (cooking) condition will experience positive changes in food agency, intuitive eating, cooking frequency, and diet quality outcomes after six weeks of cooking classes compared to students in the control condition.

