Withdrawal Procedures: Define the precise criteria for withdrawing subjects from the study. Include a description of study requirements for when a subject withdraws him or herself from the study (if applicable).

Participants may withdraw from the study at any time by notifying the PI or Study Coordinator in writing (or by email) of their intention.

If necessary, subjects may be terminated or withdrawn by the Principal Investigator without the consent of the participant if continued participation would be contraindicated, including because the participant moves more than 120 miles from the university with no plans to return during study intervention phases.

Sources of Materials: Identify sources of research material obtained from individually identifiable human subjects in the form of specimens, records or data. Indicate whether the material or data will be obtained specifically for research purposes or whether use will be made of existing specimens, records or data.

The demographic, behavioral, and self-report questionnaire data collected in this study will be obtained for research purposes only.

DRUG AND DEVICE INFORMATION

Investigators are encouraged to consult the UVM Medical Center Investigational Pharmacy Drug Service ([name]) prior to finalizing study drug/substance procedures.

Drug (s) **Not applicable**

Drug name – generic followed by brand name and common abbreviations. Availability – Source and pharmacology; vial or product sizes and supplier. If a placebo will be used, identify its contents and source. (attach investigational drug brochure)

Preparation: Reconstitution instructions; preparation of a sterile product, compounded dosage form; mixing guidelines, including fluid and volume required. Identify who will prepare.

Storage and stability – for both intact and mixed products.

Administration – Describe acceptable routes and methods of administration and any associated risks of administration.

Toxicity – Accurate but concise listings of major toxicities. Rare toxicities, which may be severe, should be included by indicated incidence. Also adverse interactions with other drugs used in the protocol regimen as well as specific foods should be noted. Address significant drug or drug/food interactions in the consent form as well. List all with above details.

Is it FDA approved: (include FDA IND Number)

1. in the dosage form specified? If no, provide justification for proposed use and source of the study drug in that form.

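### The 120-mile withdrawal rule does not separate stopping the intervention from stopping data collection, although the Hypothesis 1-3 outcomes are collected online by default

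*Combined protocol and SAP*

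**What the plan says.** Withdrawal Procedures gives the investigator a discretionary power: "If necessary, subjects may be terminated or withdrawn by the Principal Investigator without the consent of the participant" when continuing would be contraindicated, "including because the participant moves more than 120 miles from the university with no plans to return during study intervention phases". The section does not mention follow-up after removal, the analysis of people removed, or stopping the intervention while outcomes continue.

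Elsewhere the protocol describes how outcomes are obtained:

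- The questionnaires (CAFPAS, Perceived Stress Scale, Intuitive Eating Scale-2) are completed through REDCap links sent by email, with paper available on request.
- For diet, "ASA-24 logs will be administered through the ASA-24 respondent website", and the Healthy Eating Index is calculated from those recalls.
- For cooking frequency, "weekly data collection (Photo Elicitation and Cooking Frequency) will be administered through REDCap".
- The interoceptive awareness exercise is in person ("Next, we will take their wrist pulse for 30 seconds"). It is optional and takes place during Phase 1 classes.
- Five participants per group are interviewed about their photos at the end. Whether this is in person or remote is not stated.

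Under Intervention, Groups B and D receive nothing after Phase 1 but still complete surveys and data collection. For Phase 3, "Participants in groups A and C will receive an email at the beginning of each week for the next six weeks" with the recipes. A closing questionnaire asks all participants about "changes that occurred to their living situation and food access as a result of the COVID-19 outbreak".

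Statistical Considerations plans repeated measures ANOVA for Aims 1 to 3, and a generalized linear mixed model for weekly cooking frequency under Aim 1. It defines no analysis population and no missing-data rule.

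**The concern.** Ending someone's participation is different from ending their intervention. The rule permits the first for a reason that, at most, bears on the second. If it is used, outcomes that could still be obtained through an email link are lost after allocation, on a decision made by the investigator.

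The loss is unlikely to be unrelated to outcome. Study Population excludes students who live with parents or guardians because they probably have less need to cook for themselves. By that reasoning, a student whose living situation changes may also change in cooking frequency, diet or stress. Removing such people makes the remaining sample more selected, and outcomes never collected cannot be checked afterwards. The pilot is also meant to supply data for sizing a larger trial, so selective loss would carry into that calculation.

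**Working it through.** **Does distance prevent collection?** Each measure is set against its mode.

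| Measure | Hypotheses (Statistical Considerations) | Mode | Needs proximity after Phase 1? |
|---|---|---|---|
| CAFPAS (food agency) | 1, 2a, 2b | REDCap | No |
| ASA24/HEI (diet quality) | 1, 2a, 2b | ASA24 website | No |
| Weekly cooking frequency | 1, 2a, 2b | REDCap | No |
| Intuitive Eating Scale-2 | 1, 2a | REDCap | No |
| Perceived Stress Scale | 3 | REDCap | No |
| Pulse count | none | In person, optional, Phase 1 | No |
| Photo interview | not a Hypothesis 1-3 outcome | Not stated | Not stated |

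**Does delivery depend on location?** Phase 1 classes do (teaching kitchen). Phase 2 kits do (home delivery, Groups A and C only). Phase 3 recipes do not (email). Groups B and D have nothing to deliver in Phases 2 and 3, so for them distance gives no delivery reason for removal in those phases.

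**What would the analysis do with a removed person?** Assessments fall at baseline and after each of three phases, four in all. Someone removed during Phase 3 has three of the four. A conventional repeated measures ANOVA over all four uses complete cases only, so it would use none of those three. The mixed model for cooking frequency would use every week up to removal.

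**Plan's own figure.** 4 groups x 16 = 64, which reproduces. The plan gives no power, SD, effect size, dropout rate or relocation rate.

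**Illustration of bias (assumed inputs).** If a fraction f of one arm is removed, and those removed differ from those retained by g SD, the retained mean differs from the full-arm mean by f x g.

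| Removed | f | g = 0.5 SD | g = 1 SD |
|---|---|---|---|
| 2 of 32 | 0.0625 | 0.03 | 0.06 |
| 4 of 32 | 0.125 | 0.06 | 0.13 |
| 8 of 32 | 0.25 | 0.13 | 0.25 |

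If both arms lost the same share with the same g, the shifts would cancel in the between-arm comparison. With equal g, the bias in the comparison is the difference in shares times g.

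**Illustration of precision (assumed two-sided 5%, 80% power, normal approximation, no clustering).** Detectable difference = (1.960 + 0.842) x sqrt(2/n), in SD units:

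- 32 v 32: 2.802 x sqrt(2/32) = 0.70
- 28 v 28: 2.802 x sqrt(2/28) = 0.75
- 24 v 24: 2.802 x sqrt(2/24) = 0.81

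**The case against.** The case on the other side has several parts.

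- **The rule is permissive.** A long-distance move is one listed reason and not an automatic trigger, and nothing prevents the investigator from keeping a mover. That is correct. But discretion with no stated criterion for keeping people is itself part of the gap.
- **Not every measure is online.** A reader might infer that all outcomes are collected remotely. The pulse count, the unstated interview mode and the paper option show otherwise. The point is confined to the Hypothesis 1-3 measures, where it stands.
- **Nothing says earlier data are discarded.** A reader might infer that removed participants leave the analysis altogether. Withdrawal Procedures does not say so, and the data storage section keeps original files intact. Loss of earlier data would follow only from a complete-case ANOVA, which is the usual form but is not specified.
- **COVID-19.** A reader might infer that the plan expects many moves and would remove the people its closing questionnaire describes. The questionnaire looks back, goes to all participants, and fits equally well with movers being retained. Phase 2 from mid-January plus twelve weeks ends in early to mid-April, and this version carries an approval date of 4/14/2020. On that timetable the intervention phases were finished or nearly so. No document reports or predicts a removal for distance.
- **Differential removal.** The rule is worded alike for all groups, and only Biostatistics staff see raw data. Nothing in the documents shows that one arm would lose more than another.
- **Location has a real operational role** in class attendance and kit delivery. This may explain the rule, but it gives no reason to stop online outcome collection.

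**Conclusion.** The point holds in a limited form. The protocol lets the investigator end study participation for a move that does not prevent collection of the Hypothesis 1-3 outcomes, and it makes no provision for continued follow-up or for analysing those removed. Any use of the rule would produce avoidable missing data after allocation, plausibly related to outcome.

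The size cannot be computed from the documents. The shift of 0.03 to 0.13 SD in one arm's mean rests on assumed removal of 6% to 25% and an assumed 0.5 SD difference. The rise in detectable difference from 0.70 to 0.81 SD rests on assumed loss of 8 of 32 on each side, measured against a power target that this pilot never set. Neither figure shows that bias occurred. The change is worth making because it is cheap and because outcomes not collected at the time cannot be recovered.

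**What to change.** Leave any rule on intervention delivery as it is. Amend Withdrawal Procedures to state that a participant who moves:

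- remains in the study for outcomes;
- continues the online questionnaires, ASA24 recalls and weekly reports unless they withdraw consent;
- is analysed in the assigned group.

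Record the date of the move, and use it in a sensitivity analysis. In Statistical Considerations, add a sentence on the analysis population and on how incomplete follow-up is handled.

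The cost is one short amendment and continued email links that the study already sends. The downside is that some retained data will come from people who did not receive the full intervention. The recorded move date lets the analysis show how far that matters.

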Group D (n=16) – Control condition followed by no further instruction

Assessments will be conducted at baseline, and following each phase.

Aim 1: Aim 1: To pilot test a food-agency focused cooking class pedagogy to motivate college students to cook more frequently, improve their diet quality, and increase their sense of food agency.

Aim 2: To evaluate if providing students with six weeks of a meal delivery service and then six weeks of recipes after completion of cooking classes maintains gains in diet quality, cooking frequency, and food agency.

Aim 3: To positively influence participants' stress levels.

Aim 4: To explore the reasons why students cook or do not cook.

Cooking Classes: Those in the Cooking Classes Intervention groups will attend one cooking class per week for six weeks led by a trained chef and based on an established curriculum designed to increase one's food agency, or cooking confidence. Participants will cook one recipe per week as well as participant in various tastings.

Control Condition: Participants in the Control Condition will not attend weekly cooking classes. They will be instructed to cook or not cook as they usually do. They will be asked to complete baseline measures, as well as measures at the end of each intervention period.

Meal Kits: With the meal delivery service, participants will get all the ingredients they need to make a meal as well as a recipe for the meal which includes step-by-step photos. They are then responsible for doing the actual cooking of the meal. Students will all receive kits for 3 meals per week from the same delivery service and will have the option to select meals that fit their dietary needs (vegetarian, gluten free, etc.). Meal kits are designed to serve two individuals therefore students should have enough food for six meals, though they will only need to cook three times. The service used is open to the public, therefore students who enjoyed the meal kit service could opt to continue service and pay for it themselves. However, students will be instructed to wait until study completion to do so.

Recipes: Recipes will be designed by the research team, which includes three registered dietitians and a trained chef. Students will receive recipes for five healthy meals per week. Participants will need to shop, budget, and plan on their own. Recipes will accommodate major dietary preferences including vegetarian and gluten-free.

PURPOSE AND OBJECTIVES

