The target population for this study is all undergraduate students at UVM living off-campus in an independent housing arrangement where they have access to a kitchen. As most junior and senior students live off campus, we expect to recruit mostly junior and senior students. In Spring 2017 there were 2,232 juniors and 2,926 seniors enrolled at UVM, indicating that over 5,000 students could be eligible for the study. For the first two years at UVM, the majority of students live in dorms on campus and are required to have meal plans. The majority of juniors and seniors at UVM then move off campus. This time frame may encompass the first time that many students have had to consider buying and cooking food for themselves. Addressing cooking behaviors during this transition may help establish lifelong cooking habits. Participants will need to have access to a kitchen because the study examines how to influence and increase cooking behaviors. Participants may have roommates with whom they share a kitchen, however they will not be eligible if they live with parents or guardians, as in this scenario they likely have less required independence around cooking. Participants who already cook dinner at home four times per week or more will not be included in the study, as they are already cooking at home frequently and do not need to be motivated to do so. Previous research has indicated that the majority of college students do not prepare dinner even weekly, so we do not anticipate this inclusion criteria greatly restricting our sample.¹⁴

Inclusion criteria:

- Student at the University of Vermont
- Age 18-25
- Cooks dinner at home no more than 3x/week
- Access to a kitchen at home
- Lives independently (may have roommates but may not live with guardians)
- Availability during scheduled cooking classes/demonstrations

Phase 1: The Cooking Program

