Active Intervention. Six cooking classes will be held every week for six consecutive weeks. The cooking lessons will be patterned after [name] cooking pedagogy and will be tailored for individuals cooking for themselves for the first time. Classes will begin with a brief lecture on the day's topic, followed by a laboratory session. Participants work in teams of two in the NFS foods lab to actively practice skills and cook a meal. Subjects will receive recipes and information sheets that cover pantry supplies, grocery lists, knife skills and cooking equipment. Classes will be taught by a chef trained in the pedagogy by [name] and participants will have the opportunity to sample the food they prepared at the end of class.

Kitchen Intensive. As part of the orientation process, participants will attend a 2-hour kitchen intensive demonstration. This demonstration will introduce participants to the kitchen lab space and cover basic kitchen skills including food safety, sanitation, equipment overview, and the basic principles of food agency.

Control Condition. Those in the Control Condition will receive no cooking support over the fall semester. They will serve as a benchmark for how college students normally cook without focused instruction. They will be asked to fill out all measures at baseline and throughout the intervention and will be incentivized to do so.

Phase 2 and Phase 3: Follow up Support

The active and control groups receiving follow up support (groups A and C) will receive six weeks of meal kits immediately following the start of the spring semester. Participants in these groups will receive a single delivery each week that will contain three dinner meal kits designed to feed 2 people. The kits will contain all of the ingredients and instructions needed to prepare the recipes, though participants must cook the meals themselves. After six weeks of receiving meal kits, groups will receive five healthy recipes via email per week. Recipes will be designed by the research team, which includes three registered dietitians and a trained chef. Participants will need to shop, budget, and plan on their own.

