This is a pilot study with no previous data available to calculate expected statistical power. The sample size chosen was practical as our foods lab can only accommodate 16 people at a time. One group of each intervention arm (four) would give us data on approximately 64 subjects. This preliminary data will be used to determine the sample size power needed for a larger study with sufficient statistical power.

Inclusion/Exclusion Criteria: Eligibility and ineligibility criteria should be specific. Describe how eligibility will be determined and by whom. Changes to the eligibility criteria at a later phase of the research have the potential to invalidate the research.

Interested individuals will be directed to a study application that provides details about the study program and asks a series of screening questions. These questions are intended to determine basic eligibility for the study. Ineligible applicants will be notified of their ineligibility and directed to other campus resources related to cooking and meal planning. Eligible applicants will be directed to sign up for an in-person information session.

Inclusion criteria:

- Student at the University of Vermont
- Age 18-25
- Cooks dinner at home no more than 3x/week
- Access to a kitchen at home
- Lives independently off campus (may have roommates but may not live with guardians)
- Availability during scheduled cooking classes/demonstrations

Individuals will be excluded from the study if they do not complete baseline data collection measures prior to the first class meeting. Baseline data measures include four questionnaires (PSS, CAFPAS, Cooking Behavior, and intuitive eating scale), three days of ASA-24 logs, one photo elicitation survey, and one cooking frequency survey.

Inclusion of Minorities and Women: Describe efforts to include minorities and women. If either minorities or women are excluded, include a justification for the exclusion.

Women and minorities will be included. During recruitment, we will work with UVM Office of Student and Community Relations to ensure that our recruitment materials and procedures capture eligible students of all demographics.

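### Two housemates can enrol and be placed in different groups, so home-delivered two-person meal kits and emailed recipes can reach Group B or D students who are analysed as unsupported.

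*Combined protocol and SAP*

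**What the plan says.** **Eligibility.** The list under Inclusion/Exclusion Criteria has "Lives independently off campus (may have roommates but may not live with guardians". Study Population adds: "Participants may have roommates with whom they share a kitchen". Neither inclusion list restricts the number of participants per household, and no household question is described for the online application.

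**Assignment.** Under Procedures, class participants are placed in class periods by availability, and a random table then decides which periods get follow-up. Control students are randomised to follow-up or none. On balance between groups the text says: "Groups will not be stratified by any criteria, and instead will be determined based upon participant availability". Under Consent Procedures, control students are invited from those who applied for the classes but went no further, so both sides come from one applicant pool.

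**Support.** Under Phase 2 and Phase 3: Follow up Support, the weekly delivery to Groups A and C "will contain three dinner meal kits designed to feed 2 people". Under Intervention, the kits go to students' "homes once per week and will include the ingredients and instructions for preparing 3 separate meals". Phase 3 follows: "Participants in groups A and C will receive an email at the beginning of each week for the next six weeks", with five recipes each time. The Meal Kits paragraph near the start treats the second portion as the participant's own: "Meal kits are designed to serve two individuals therefore students should have enough food for six meals". Sharing is neither forbidden nor recorded. The nearest restriction asks students not to buy the service themselves until the study ends.

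**Analysis.** Under Statistical Considerations, repeated measures ANOVA compares material support with no support, and a generalised linear mixed model handles weekly cooking frequency. Neither has a household term.

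**The concern.** Hypothesis 2a needs Groups B and D to be without cooking support during Phases 2 and 3. A Group B or D student who shares a kitchen with a Group A or C student can eat kit dinners, cook alongside the housemate and use the recipes, yet be counted as unsupported. For diet quality and food agency this would tend to move the unsupported groups toward the supported ones and understate the effect.

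The Sample Size section says the pilot data will be used to size a larger study. A diluted effect would therefore carry forward into that calculation. Because nothing on household or sharing is collected, the analyst could not tell afterwards whether it had happened.

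**Working it through.** **Inputs from the documents**
- Four groups of 16: 4 × 16 = 64, which reproduces the stated total. Groups A and C (supported) number 32; Groups B and D (unsupported) number 32.
- Support per supported student: 3 kits × 6 weeks × 2 portions = 36 portions, then 5 × 6 = 30 recipes.

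**Assumptions, because the documents give no figure**
- k, the number of enrolled housemate pairs: 2, 4 or 8.
- s, the share of the effect passed to an exposed housemate: 0.5.
- Housemates fall among the four groups at random.

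**Step 1. Chance that a pair is split supported/unsupported.** There are 64 × 63 / 2 = 2016 possible pairs, of which 32 × 32 = 1024 have one supported and one unsupported member. 1024 / 2016 = 50.8%.

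The actual procedure is not a single random placement of 64 people, so this was checked by type of pair. For two control students randomised 16 and 16, the chance is 16 × 16 / (32 × 31 / 2) = 256 / 496 = 51.6%. For one class and one control student, the A–D and B–C combinations together give 50% if each side's draw is even. For two class students it depends on the class periods they choose, and it is zero if they share a period.

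**Step 2. Exposure and attenuation.** Expected split pairs = k × 0.508. Exposed share p = split pairs / 32. Attenuation = p × s. Required sample size varies as 1/d², so a larger study planned on the diluted effect is inflated by 1/(1 − p × s)².

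| Pairs k | Split pairs | p | Attenuation (s = 0.5) | Inflation of later N |
|---|---|---|---|---|
| 2 | 1.0 | 3.2% | 1.6% | 1.03 |
| 4 | 2.0 | 6.3% | 3.2% | 1.07 |
| 8 | 4.1 | 12.7% | 6.3% | 1.14 |

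**Step 3. What a larger exposure would require.** For p = 10%, 0.10 × 32 = 3.2 exposed students, and 3.2 / 0.508 is about 6 pairs. For p = 25%, 0.25 × 32 = 8 exposed students, and 8 / 0.508 is about 16 pairs, or 32 of the 64 participants. The second is an extreme case.

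**Step 4. Which contrast is exposed.** Phase 1 is set for October 2019 and the kits for mid-January 2020, with recipes after them. Hypothesis 1 is assessed after the six weeks of classes, before any kit or emailed recipe exists. It is exposed only through the recipes and information sheets handed out in class.

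**Step 5. Direction by outcome.** The weekly survey counts how often the participant cooked at home. A Group B or D student who eats a housemate's kit dinner may cook less, which would widen the difference; one who cooks alongside or borrows recipes may cook more, which would narrow it.

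**The case against.** The strongest reply is that nothing shows housemates enrol together. Recruitment is by emails, class social media, flyers and campus tables. With two to four pairs the dilution is a few per cent at most, in a capacity-limited pilot that claims no power. Housemates with similar timetables may also choose the same class period and land together. All of this stands: it limits the size and makes the point a possibility. It does not remove the gap, because no rule prevents split households and no planned data would reveal them.

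A reader might infer four stronger things, none of which the documents support:
- **That the kits are meant to be shared.** The protocol assigns the second portion to the participant as an extra meal. Sharing is possible, but it is not the design.
- **That kits and recipes also bias the fall class-versus-control contrast.** The timetable rules this out. The handout route is weaker, since the treatment is weekly two-hour hands-on classes and the protocol's own background argues that passive information changes little.
- **That every outcome is biased toward no difference.** For cooking frequency the sign is uncertain.
- **That a quarter of the unsupported students could readily be exposed.** On the random-placement assumption that needs about half the sample to be housemate pairs.

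A further fair point is timing. This version carries an approval date of 14 April 2020, after the planned start of Phases 1 and 2, so an eligibility change may come too late for this cohort.

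**Conclusion.** The point holds as a gap in design and data collection. Split households are possible, the support is easy to pass on within a kitchen, and nothing prevents, records or adjusts for it. The exposed comparison is Groups A and C against Groups B and D under Hypothesis 2a. Group C, although a control group in Phase 1, is itself supported later. The likely effect is some dilution in diet quality and food agency, of a size the documents cannot settle. The range of 1.6% to 6.3% rests on the assumed number of pairs, random placement and half the effect being passed on. It is worth correcting because prevention is cheap and the results are meant to inform a larger trial. It is not evidence that the comparison has been compromised.

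**What to change.** **If enrolment is open.** Add one household question to the online application, and add to both inclusion lists (Study Population and Inclusion/Exclusion Criteria) that one student per household is accepted. Only if a seat would otherwise go unfilled, admit a housemate into the same group: the same class period on the class side, or one draw per household on the control side. Either route removes split pairs, so p = 0 and the total stays at 64.

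**If enrolment has closed.**
- Add items to the end-of-study COVID-19 questionnaire, which already asks about changes in living situation: whether a household member took part in the study, and whether kit meals or recipes were shared. Ask separately for Phases 2 and 3, because living arrangements may have changed between them.
- Run a sensitivity analysis of Hypothesis 2a without Group B or D students who live with a Group A or C participant. With perhaps one to four students removed, it shows whether the estimate moves but cannot prove that there was no sharing.
- Carry the one-per-household rule into the larger study.

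**Cost.** One criterion and one application question, or a few questionnaire items and one extra analysis. A few applicants may be lost. The protocol's figure of over 5,000 potentially eligible students counts juniors and seniors before the other criteria are applied. The loss would be felt most on the control side, which is drawn only from applicants who did not proceed to the classes.
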